9.3. Study Medical Monitor Enrollment Consultation

The Investigators are encouraged to consult with the Study Medical Monitor in cases where the Screening or Day 1 Visit findings suggest that the subject may have a medical condition that is unstable or liable to obfuscate the safety data collected. Below are examples of such laboratory and ECG findings.

1. Clinical laboratory findings:
 - a. Both ALT and AST are above the upper limit of normal
 - b. Hemoglobin <11 gm/dL, platelet count <125,000/mL, or a low neutrophil or lymphocyte count

- c. Microscopic hematuria, proteinuria, or pyuria
 - d. Glucose >250 mg/dL
2. Electrocardiographic findings:
- a. Left bundle branch block
 - b. Bifascicular block – right bundle branch block with either left anterior or left posterior hemiblock
 - c. PR interval >220 msec
 - d. QTcF >470 msec
 - e. Atrial fibrillation

9.4. Subject Replacement

Enrolled subjects who prior to completion of the Week 8 Visit are: (a) terminated by the PI or completely withdraw themselves from the study, (b) declared a violator or major deviator, or (c) lost to follow-up, may be replaced at the discretion of the Sponsor.

9.5. Subjects Leaving the Trial

Subjects who are terminated or who withdraw from the trial will be asked to complete Week 12 assessments (see Early Termination Visit, Section 12.6.4). Women will also be asked to undergo β -HCG testing at that time.

9.5.1. Termination by the Investigator

The Investigator may terminate a subject from the study at any time, due to: (a) trial misconduct, (b) violation of the rules of the site, (c) protocol violation; (d) pregnancy, or (e) unexpected personal issues that arose during the trial. Terminations must be reported verbally and in writing to the Study Medical monitor within 24 hours.

In addition, if an Investigator (or designee) believes that the current dosing may be detrimental to a subject's well-being, that subject may be offered any of the options discussed in Section 7.4 (Dose Holidays and Adjustments) following consultation with the Safety Medical Monitor.

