7.5. Study Withdrawals and Discontinuations

Subjects may **withdraw** their consent from participation in the study at any time. The date and reason for withdrawal should be recorded.

Subjects who wish to **withdraw** from the study due to an AE related to the study drug should be encouraged to remain in the study and consider the options offered in Section 7.4 instead of withdrawing completely from the study. Subjects who decide to **withdraw** from the study should be encouraged to undergo Early Termination Visit assessments (Section 12.6.4).

Subjects who permanently **discontinue** applying their study drug for any reason (whether on their own initiative or at the behest of the investigator) should be encouraged to remain in the trial (not to withdraw consent from participation) so they may undergo the remaining trial procedures and assessments. The date and reason for the study drug discontinuation should be recorded.

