8. STUDY ENDPOINTS

Primary Efficacy Endpoints:

- Percentage of subjects achieving complete clearance of AK lesions within their Treatment Field on Week 16
- Percentage of subjects with facial Treatment Fields achieving complete clearance of AK lesions on Week 16

Secondary Efficacy Endpoints:

- Percentage of subjects achieving partial ($\geq 75\%$) clearance of AK lesions within their Treatment Field on Week 16
- Percentage of subjects with facial Treatment Fields achieving partial ($\geq 75\%$) clearance of AK lesions on Week 16
- Change from baseline in the number of AK lesions in the Treatment Field of each subject by Weeks 16
- Change from baseline in the number of facial AK lesions in the Treatment Field of each subject by Weeks 16

Safety Endpoints:

- AEs, clinical laboratory parameters, vital signs, physical examinations, Local Skin Reaction (LSR) Scores, electrocardiograms, and drug exposure.

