12. CONDUCT OF THE STUDY

12.1. Study Blinding and Randomization

12.1.1. Study Blinding

This is an open-label study. Therefore, no one will be blinded.

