12.6.4. Early Termination Visit

Subjects exiting the study before completion of the Treatment Period should undergo Early Termination Visit assessments. The following assessments will be performed during such a visit.

- Adverse event(s) AEs will be recorded
- Concomitant medications documented
- Vital signs: peripheral blood pressure, respiratory and heart rates, and oral temperature will be recorded
- Physical examination
- Local Skin Reaction Score in the Treatment Field
- AK Lesions in the Treatment Field: count (11.1.1)
- 12-lead ECG tracing recorded pre-dose. An original (duplicate) copy of each ECG is required. This ECG will also be transmitted to the central ECG laboratory

- Clinical laboratory tests including hematology, chemistry, coagulations, and urinalysis: Fasting status to be recorded
- Study drug accountability and dosing compliance: study drug tubes will be weighed and the results recorded. Dosing Diaries will be collected. **Neither study drug nor Dosing Diaries will be returned to the subject.**
- Urine Pregnancy Testing will be performed on all women and results recorded.

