17.7.2. Modified ITT (mITT) Population

The modified Intent-to-Treat (mITT) population will be defined as all subjects who are enrolled into the study, received any study drug, and did not fail Exclusion Criterion #2. Subjects in this population will be analyzed according to the cohort to which they were allocated. All efficacy analyses will be performed on the mITT population.

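### Dosed subjects whom the investigator terminates from the study stay in mITT, but no section asks them back for the Week 16 count that defines the primary endpoint.

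*Combined protocol and SAP*

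**What the plan says.** Section 9.5.1 gives the investigator a power over study participation: "The Investigator may terminate a subject from the study at any time, due to" misconduct, breach of site rules, and then "c) protocol violation; (d) pregnancy, or (e) unexpected personal issues that arose during the trial". Subjects who themselves wish to leave are handled separately, in 9.5.2. For those who go, section 9.5 says "Subjects who are terminated or who withdraw from the trial will be asked to complete Week 12 assessments", with a pointer to 12.6.4. That section is narrower: "Subjects exiting the study before completion of the Treatment Period should undergo Early Termination Visit assessments". Its list includes a lesion count but no later visit.

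Section 7.5 takes the opposite line for subjects who permanently stop drug, including when the investigator asks for it. They "should be encouraged to remain in the trial (not to withdraw consent from participation) so they may undergo the remaining trial procedures and assessments".

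The first primary efficacy endpoint in section 8 is "Percentage of subjects achieving complete clearance of AK lesions within their Treatment Field on Week 16"; the second is the same outcome in subjects with facial fields. Section 17.7.2 defines mITT as "all subjects who are enrolled into the study, received any study drug", with one exception, failure of Exclusion Criterion #2. A Week 16 count is not a condition of membership. Section 17.6 leaves missing data to a SAP whose rule is not in the supplied text. On blinding, 12.1.1 says: "This is an open-label study. Therefore, no one will be blinded".

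**The concern.** The plan counts a group of subjects in its main efficacy population while a separate clause ends the measurement needed to classify them. The subject may be willing to continue; the decision belongs to the investigator. The investigator or designee counts the lesions at Weeks 4, 8 and 12 and knows the regimen. If the power is used, the Week 16 outcome is missing by decision and not by accident, and a missing-data rule can only impute it. At stake is the completeness of each cohort's Week 16 clearance percentage and its Clopper-Pearson interval (17.3.1), which are among the results that section 5.6.4 says will inform Phase 3 design and dose selection.

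**Working it through.** **Step 1. Follow one subject through the text.** Take a dosed subject, still consenting, whom the investigator terminates at about Week 6.

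- Section 9.5.1: participation in the study ends.
- Sections 9.5 and 12.6.4: an Early Termination Visit with Week 12 procedures, including a lesion count, is requested. In Table 1 this visit shares a column with Week 12, although it takes place whenever the subject leaves.
- Weeks 13 and 16: no request in 9.5, 9.5.1 or 12.6.4.
- Section 17.7.2: the subject stays in mITT unless Exclusion Criterion #2 was failed.
- Section 8: the outcome needed is clearance at Week 16 (Day 113 ±5 in Table 1). It does not exist.

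Now let the same subject stop drug at the investigator's request without being terminated. Section 7.5 applies and the Week 16 count is sought. Section 7.5 does not limit 9.5.1, and no criterion says when a willing subject should follow one path or the other.

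**Step 2. Exits between Week 12 and Week 16.** Section 12.6.4 covers only exits before the Treatment Period is complete, so it describes no visit for a later termination. Section 9.5 still points such a subject to Week 12 assessments.

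**Step 3. What protocol violation means.** Section 17.8 defines a violation as an enrolled subject who does not meet the enrollment criteria; departures from procedure are deviations. Section 17.7.3 removes violators from Per Protocol. Except for Exclusion Criterion #2 failures, mITT keeps them, so it is the mITT analysis that needs their Week 16 count.

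**Step 4. Size.** Section 17.1 reports no formal sample size calculation, so there is only the enrolment arithmetic to reproduce.

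- Per cohort: 40 + 70/2 = 75. Total: 40 + 40 + 70 = 150. Both agree with the plan.
- Allowance for subjects without data, from any cause: 75 − 70 = 5, and 5/75 = 6.7%.
- Effect of one missing subject on a cohort's mITT rate: 1/75 = 1.3 percentage points between counting the subject as cleared and as not cleared.
- Facial endpoint: if about 75% have facial fields, as in the earlier Phase 2 study (5.5.2), 0.75 × 75 ≈ 56, and 1/56 = 1.8 points.

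The plan gives no expected clearance rate. The table assumes rates of 20%, 30% and 40% among 70 observed subjects, with 5 of 75 missing:

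| Observed | Missing as not cleared | Missing as cleared |
|---|---|---|
| 14/70 = 20.0% | 14/75 = 18.7% | 19/75 = 25.3% |
| 21/70 = 30.0% | 21/75 = 28.0% | 26/75 = 34.7% |
| 28/70 = 40.0% | 28/75 = 37.3% | 33/75 = 44.0% |

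The spread is 5/75 = 6.7 points whatever the rate. For scale, the 95% Clopper-Pearson interval for 21/75 runs from 18.2% to 39.6%, a width of 21.4 points. The 6.7 points would apply if all five losses came from this clause, which nothing in the plan says.

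**The case against.** The case for leaving the text alone has real force.

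- A reader might infer that any non-adherence can get a subject removed. Under 17.8 it cannot, if the term carries that section's meaning: a violation is an eligibility failure, and the sponsor decides the classification. Section 9.5.1 does not refer to 17.8, so a looser use is possible, but the defined meaning is the fair one. Eligibility is settled by Day 1 and has no evident link to later response.
- A reader might also infer that investigators would remove poor responders. Lack of efficacy is not a listed ground, every termination must be reported to the medical monitor within 24 hours, and concerns about dosing are sent to the options in 7.4. Only the personal-issues ground is loosely worded, and some of those subjects could not attend Week 16 anyway.
- The power is permissive, and an exit count is requested, so some efficacy data will exist. No passage says that this count stands in for Week 16; the shared column in Table 1 is a layout choice.
- Efficacy is descriptive, and tolerance and safety also feed the Phase 3 decision.

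All of this stands and limits the claim. It does not answer the central gap: no section asks a willing, dosed, terminated subject to return at Week 16, and no later missing-data rule can recover a count that was not taken.

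**Conclusion.** The gap is real and modest. It creates avoidable missing primary outcomes inside mITT, at 1.3 points per subject for the overall endpoint and about 1.8 for the facial one if the earlier study's facial share holds. Selective loss is possible because the study is open label and one ground is elastic. The documents do not show that it will happen, and they state neither a termination rate nor a link with response. It would be wrong to attach the full 6.7 points to this clause, because the 5-of-75 margin also has to absorb withdrawal and loss to follow-up. The conclusion rests on the wording of 9.5, 9.5.1 and 12.6.4, and on no separate follow-up rule existing outside the supplied text. It is a cheap improvement to data collection and not a flaw that undermines the design.

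**What to change.** Leave the grounds for termination and every decision about study drug unchanged. Reconcile 7.5, 9.5, 9.5.1 and 12.6.4 by adding two statements:

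1. Any subject who received study drug, is terminated by the investigator, has not withdrawn consent and can attend safely will be asked to return at Week 16 for the scheduled lesion count with the adverse event and local skin reaction check. This applies equally to terminations after the Treatment Period.
2. The Early Termination count is recorded under its actual date and does not replace the Week 16 count.

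The cost is amendment wording and one or two already scheduled visits for a few subjects. Some will decline or be unable to attend, so the SAP still needs its missing-data rule.

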9.5.2. Subjects Who Wish to Withdraw

If a subject who received at least 1 dose of the study drug wishes to withdraw from the trial, that subject may be offered any of the options discussed in Section 7.4 (Dose Holidays and Adjustments). These options may be offered without prior consultation with the Study Medical Monitor.

Subject withdrawals must be reported verbally and in writing to the Study Medical Monitor within 24 hours.

If a subject withdraws consent from the study, all data and samples (blood, urine, ECGs, etc.) collected prior to the time of withdrawal will be analyzed and the data will be included in the trial data base.

9.5.3. Subjects Lost to Follow-Up

In the case of a subject lost to follow-up, attempts to contact the subject must be made and documented in the subject's files.

10. PROCEDURES FOR SAFETY EVALUATIONS

10.1. Medical History

Medical history, including any diseases, all past surgeries including skin procedures, and psychiatric illnesses will be documented.

Each subject will be questioned regarding any planned elective procedures that may occur during or following completion of the study, and these must be documented in the subject's medical record and the medical history section of the CRF.

10.2. Prior Concomitant Medications

All medications or medical products taken by the subject within 2 months prior to Screening, whether the subject has stopped the medication or whether the subject has continued taking the medication, will be recorded as a Prior Concomitant Medication. This also includes medications taken prn.

All topical skin treatments (i.e., medicinal or physical) received in the 4 months prior to Screening will be recorded.

10.3. Safety Measures

10.3.1. Adverse Events

The investigator will determine at each study visit whether any AEs have occurred. Sections 15 and 16, respectively, contain additional information regarding AEs and SAEs.

10.3.2. Vital Signs, Weight, and Height

Throughout the study, vital signs (resting blood pressure, heart rate, temperature, and respiratory rate) will be obtained with the subject sitting or lying, after the subject has rested for at least 2 minutes.

Heart rates are best obtained electronically, if available. If heart rate data are obtained electronically, the results may not be obtained from an ECG scheduled at the same time. If these data are obtained manually, a minimum observation period of 30 sec is required.

Respiratory rate will be determined following a minimum observation of 30 sec.

The subject's height and weight will be documented during the Screening visit.

10.3.3. Physical Examination

The physical examinations performed during the trial will include skin, external eyes, oral cavity, nodes, lungs, heart, abdomen, and extremities.

The investigator will also be asked to assess whether the following neurologic functions are normal / abnormal.

1. Mentation: appropriate behavior; logical thought processes

2. Motor: use of all 4 extremities
3. Cerebellar: gait; balance standing and sitting
4. Cranial nerves: speech, facial symmetry, and hearing

If any of these is abnormal or changed from baseline, the Investigator will be asked to describe the findings.

All abnormal acute and chronic findings on physical examination must be recorded whether they are new or were recorded previously in the medical records of the subject. For example, a surgical scar should be recorded on every scheduled physical examination.

AK lesions that are outside the Treatment Field must be recorded in the physical examination. This applies to AK lesions on the head or on any other part of the body. However, only lesions that require treatment at the time of the examination should be considered clinically significant. Please refer to Section 12.9.1 regarding which AK treatments are allowed and prohibited during the trial.

All other skin lesions must be reported on the physical examination. However, only skin lesions that require treatment at the time of the examination should be considered clinically significant.

10.3.4. Clinical Laboratory Tests

Blood and urine sampling will be collected and sent for analysis to CRL the central laboratory and will occur as listed in Section 12.6 and the Table of Study Assessments (Section 7.3). All blood samples will be drawn, prepared, and maintained as per central laboratory manual. Blood sampling for all clinical laboratory tests should be performed following a fasting period of approximately 8 hours with the exception of the Screening blood sampling that may be performed randomly (i.e., with or without fasting). The fasting status of the subject will be recorded.

The following tests will be performed as part of the Clinical Laboratory Tests:

- a) **Hematology:** The hematology analysis will consist of the following tests:
 - White Blood Cell Count
 - White Blood Cell Differential in absolute numbers only (not percent)
 - Hemoglobin
 - Hematocrit
 - Mean Corpuscular Volume (MCV)
 - Mean Corpuscular Hemoglobin Concentration (MCHC)
 - Red Blood Cell Count
 - Platelet Count
- b) **Coagulation Profile:** The coagulation parameter analysis will consist of the following tests:
 - Prothrombin Time (PT) and/or International Normalized Ratio (INR)
 - Activate Partial Thromboplastin (aPTT)

c) **Complete Clinical Chemistry:** The Complete Clinical Chemistry consists of the following tests:

- ALT
- AST
- Albumin
- Alkaline phosphatase
- Direct bilirubin
- Total bilirubin
- Blood urea nitrogen or urea
- Calcium
- Total cholesterol
- Chloride
- Creatinine
- Glucose
- Lactate dehydrogenase
- Inorganic phosphorus
- Potassium
- Total protein
- Sodium
- Triglycerides
- Uric acid
- Total CPK
- Glomerular filtration rate, estimated (as per the clinical laboratory's SOPs)

d) **Urinalysis:** The urinalysis consists of the following tests:

- Glucose
- Protein
- pH
- Ketones
- Erythrocytes
- Leucocytes
- Nitrites

10.3.5. Urine Pregnancy Test

Pregnancy testing will be performed on urine samples to be processed, assayed, and reported by site personnel.

All women enrolled in the trial must have a negative urine pregnancy test at their Screening and Day 1 Pre-Dose Visits before they can proceed to Day 1 Dosing.

10.3.6. Electrocardiogram

A standard, surface 12-lead ECG will be obtained as per the central ECG laboratory's manual at the time points listed in the Schedule of Assessments (7.3).

ECGs recorded, transmitted to the central ECG laboratory, and interpreted by that laboratory. The QT interval results will be adjusted for rate using the Bazett (QTcB) and Fridericia (QTcF) corrections.

Cardiac dysrhythmias will be documented by occurrence (date and time), severity, type, and duration. Isolated premature ventricular contractions and supraventricular extra-systolic waveforms will not be considered clinically significant.

Two printouts (original copies) of each electrocardiogram will be stored in the subjects' medical records. ECGs will be assessed, signed, and dated by the Investigator (or designee). The Investigator's initial assessment is for purposes of screening and safety follow-up only.

The Investigator's findings will be included in the final data base for insertion into listings. However, these findings will **not** be tabulated, included in summary statistics, or considered the official reading of record for purposes of study safety assessments.

All ECGs will be electronically transmitted to the central ECG laboratory for interpretation. The central ECG interpretation overrides the investigator's and will be considered the official reading of record for purposes of study safety assessments.

10.3.7. Local Skin Reaction Score

The Investigator (or designee) will use the Local Skin Reaction (LSR) Score (see Section 22.1) to numerically assess the overall degree of erythema, edema, weeping / exudate, vesicles, erosions / ulcerations, scaling / dryness, scabbing / crusting as well as the Subjective LSR Score (Section 0) to assess itching and pain in the Treatment Field. The assessments will use a 5-point scale, from 0 (none/trace) to 4 (extreme). This assessment will be performed on Day 1 Visit and repeated at each subsequent visit. The individual scores for each potential finding will be recorded in the respective cells by the assessor.

Whenever possible, the same investigator should perform all of these assessments.

In this trial LSRs will be collected independent of AEs. Details regarding LSR reporting are included in Section 15.1.

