5.4.2. Topical dermal toxicity studies in male and female minipigs

- *28-day repeat dose with a recovery phase and toxicokinetics*

In the 28-day minipig study, there were no noteworthy systemic toxicity effects observed following once-daily dermal application of VDA-1102 ointment to 10% of their body surface area, even at the highest strength tested of 20%, which is also the maximum feasible dose in this formulation. The NOAEL for systemic toxicity was thus 20% VDA-1102 ointment, corresponding to a topical dose level of 60 mg/kg/day (HED 43 mg/kg/day). The NOAEL for local application site effects was 5% VDA-1102 ointment. The only notable findings were observed in animals treated with 10% and 20% VDA-1102 ointment, where very slight to slight erythema was reported, that progressed after approximately 2 weeks to mild/moderate erythema, edema, desquamation, and/or scabs. These findings appeared to be reversible with cessation of the treatment. A maximum tolerated dose (MTD) for the local application of VDA-1102 was not reached even at the highest dose tested of 20%.

- *13-week repeat dose with a recovery phase and toxicokinetics*

A 13-week study was conducted to evaluate the potential toxicity of VDA-1102 when administered on the skin in male and female minipigs after daily unoccluded topical administration to 10% of the body surface area at concentrations 2.5, 5 and 15% of VDA-1102 ointment (corresponding to 7.5, 15, and 45 mg/kg/day, HED 11, 21, and 32 mg/kg/day, respectively). No treatment-related changes of significance were observed in mortality, clinical signs of systemic toxicity, body weight, food consumption, ophthalmoscopy, electrocardiography, clinical pathology investigations, organ weights, or macroscopic/microscopic examinations apart from changes at the dermal application site.

Erythema (sometimes multifocal) at the treatment site of similar magnitude and severity were observed in both VDA-1102-treated and vehicle control animals. Erythema was of similar magnitude and severity in all treatment groups with a mean severity score of “very slight” to “slight/well-defined.” In single cases and for a limited period of time, “moderate” erythema was observed. On occasion crust/scabs accompanied the erythema, particularly in animals receiving 15%VDA-1102. In addition, dose-related “very slight” edema was only occasionally observed in animals receiving VDA-1102.

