Skin reactions, in general, appeared within the first two weeks of the study, increased up to Week 4 and remained stable or showed a tendency to a slight improvement thereafter. During recovery a clear trend to recovery was observed and a complete recovery was noted at Week 4 of the recovery period.

The undetectable (or very low) concentrations of VDA-1102 measured on Day 1 and the low blood levels detected on Week 13 along with the low concentrations of jasmonic acid detected on Day 1 and the large exposure to this metabolite measured on Week 13, suggest that VDA-1102 is slowly absorbed from the skin of the minipigs and rapidly metabolized. The Week 13 jasmonic acid systemic exposure in minipigs following dermal application of 5% VDA-1102 in the present study was comparable to that obtained in minipigs receiving 5% VDA-1102 for 4 weeks in a previous study (RTC Study A0608), suggesting that at this dose level, there is no accumulation with an increase in duration of topical application.

The NOAEL (No Observed Adverse Effect Level) for systemic toxicity was 15% VDA-1102, the highest concentration tested. The NOAEL for the local effects was 5% VDA-1102 (15.2 mg/kg/day).

As discussed below in Section 5.7, the relative doses of VDA-1102 fed to rats and applied to the skin of minipigs were significantly higher than the exposures in the current planned clinical study.

Full details of the non-clinical studies performed to date are found in the accompanying Investigator's Brochure.

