7.4. Dose Holidays and Dosing Adjustments

If for any reason a subject or an Investigator decides to alter the prescribed dosing of the study drug due to a local skin reaction and/or AE, subjects may be offered the following options at the Investigator's discretion.

- a) Subjects may be offered to continue the study drug, adding a bland moisturizer. The bland moisturizer should be applied no sooner than 6 hours after dosing and the Treatment Field should be washed with mild soap before the next study drug application.
- b) Subjects may temporarily stop the study drug for up to 7 days and to re-assess within that period;
- c) Subjects may be offered to reduce the dosage, for example from 200 mg to 150 mg per once-daily application;
- d) Subjects applying the study drug BID may be offered to apply their medication once-daily while subjects applying the study drug QD may be offered to apply their study drug every other day; and/or
- e) Subjects may be offered to stop the study drug permanently.

Subjects may be offered one of the above options or combinations thereof.

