- Concomitant medications documented
- Treatment Field selection/confirmation
- The Treatment Field photograph, Map, and Template will be prepared.
- Supervised study drug measurement and application training (see Section 13.6.3). Subject will be trained to measure (using placebo ointment on the Dosing Card) and to accurately apply the study drug, without actually applying placebo ointment to their Treatment Field.
- Physical examination (Section 10.3.3)
- Local Skin Reaction Score of the skin around the AK lesions in the Treatment Field (baseline)
- AK Lesions in the Treatment Field: baseline count (Section 11.1.1)
- Clinical Laboratory tests including hematology, chemistry, and urinalysis. Fasting status should be recorded.
- Urine beta-HCG test will be performed on all women and results recorded.
- 12-lead ECG tracing will be recorded. An original (duplicate) copy of the ECG is required for trial documentation. This ECG will also be transmitted to the central ECG laboratory
- Repeat supervised study drug measurement and application training (see Section 13.6.3) will occur a 2nd time at the end of the Day 1 Pre-Dose Visit. Subject will be tested as to whether they can measure (using placebo ointment on the Dosing Card) and to accurately apply the study drug, without actually applying placebo ointment to their Treatment Field. Subjects (or their dosing partners) who fail to measure and/or apply the study drug properly will be screen failed.
- Enrollment criteria and safety data (from Screening and all available data from the Day 1 Pre-Dose Visit) will be reviewed and approved by the Investigator (or designee)

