12.7. Once-Monthly Subject Contact

Site personnel will contact each subject between study visits. These phone calls should be made, whenever possible, approximately 2 weeks after the Day 1, Week 4, Week 8, and Week 13 Visits. The goals of this contact are: (a) to review the dosing instructions and Dosing Diary with each subject; (b) to answer any questions raised by the study participants; (c) to remind subjects of their upcoming site visit and any related activities; (d) to remind subjects to bring their study drug to each site visit; and/or (e) to ask subjects not to take their dose on site visit days since the study drug dose on those days will be applied under the supervision of site personnel.

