12.8. Unscheduled Visits

Investigators will invite subjects to attend an unscheduled visit to the investigative site (a) if during the trial a subject's medical condition warrants more frequent observations than prescribed by the clinical protocol and/or (b) if a subject has an AE that has not stabilized or resolved and requires additional visits or follow-up beyond the standard study days.

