15.1.2. Local Skin Reactions

In this trial Local Skin Reactions (LSRs) will not be recorded as AEs unless they (a) require treatment with a prescribed medication; (b) extend >2 centimeters beyond the border of the Treatment Field; or (c) require a study drug dose adjustment.

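### No skin score or skin question is scheduled between the Day 1 baseline and Week 4, so short early reactions can be missed and dose-cut reactors can lack a peak LSR grade

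*Combined protocol and SAP*

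**What the plan says.** - **Timing of the score.** Section 10.3.7: "This assessment will be performed on Day 1 Visit and repeated at each subsequent visit". Section 12.6.1 places the Day 1 score in the Pre-Dose Visit. The Day 1 Dosing Visit in 12.6.2 lists none. The next visit is Week 4, at Day 29 ±4 in Table 1 and ±5 in 12.6.2.
- **Contact in between.** There is one call, at about Week 2. Section 12.7 begins its list: "The goals of this contact are: (a) to review the dosing instructions and Dosing Diary with each subject". The other goals are to answer subjects' own questions, remind them of the visit, remind them to bring the drug, and ask them not to dose before a site visit. AEs are determined at study visits (10.3.1).
- **When a skin reaction is an AE.** Under 15.1.2, LSRs "will not be recorded as AEs unless they (a) require treatment with a prescribed medication", spread more than 2 cm past the field, or need a dose adjustment.
- **Dose changes.** Section 7.4 allows a hold, a lower dose, less frequent dosing or a permanent stop. On the hold it says: "Subjects may temporarily stop the study drug for up to 7 days and to re-assess within that period". It does not ask for an LSR score first.
- **Unscheduled visits.** Section 12.8: "Investigators will invite subjects to attend an unscheduled visit to the investigative site". It gives the reasons for such a visit but lists no procedures, and Table 1 has no column for it.
- **Analysis.** Section 17.4 says that LSR scores will be summarised, and 17.2 summarises by cohort and visit where appropriate. No maximum score is named. Dose adjustments and AE intensity are also summarised.

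**The concern.** Local skin tolerability is part of a primary objective (Section 6), and 5.6.4 says that the results will inform Phase 3 dose selection. The first four weeks are when the nonclinical data lead one to expect reactions to develop. In the 13-week minipig study: "Skin reactions, in general, appeared within the first two weeks of the study, increased up to Week 4 and remained stable". In the 28-day study at 10% and 20%, the strengths used here, slight erythema "progressed after approximately 2 weeks to mild/moderate erythema, edema, desquamation, and/or scabs".

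Two kinds of information can be lost. One is the short, field-confined reaction that has gone by Week 4 and met none of the AE conditions. The other is the peak LSR grade of a subject whose dose was held, cut or stopped before Week 4. That subject enters the Week 4 column after the dose came down, so the column can look milder than the experience it stands for. The effect could differ between 10% BID and 20% QD, the comparison that the trial is meant to inform.

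**Working it through.** The plan has no stated figure to reproduce here, and no formal sample size calculation was done (17.1).

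**1. Length of the gap.** Day 29 − Day 1 = 28 days, or 24 to 32 with ±4 and 23 to 33 with ±5. Share of treatment: 28/84 = 33%. Applications before the Week 4 score: 28 × 2 = 56 in Cohort 1 and 28 × 1 = 28 in Cohort 2. Phase 2a had visits on Days 7, 14 and 28 (5.5.2), so its longest gap in the first four weeks was 14 days.

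**2. Dose relative to Phase 2a.** Phase 2a, upper arm: 200 mg × 10% × 1 = 20 mg of drug a day. Here: 200 mg × 10% × 2 = 40 mg, or 200 mg × 20% × 1 = 40 mg. Phase 2a therefore ran at half the present daily dose.

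**3. Chance that a reaction is still present at Week 4 (illustration).** Let onset be uniform over a window of L days, duration be D, and the visit be uniform over Days 25–33 (Day 29 ±4). A reaction ending on day e is seen with probability 0 if e < 25, (e − 25)/8 if e lies between 25 and 33, and 1 if e > 33. Average this over e = onset + D.

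Example: onset Days 1–14 (L = 13) and D = 21 give e uniform on 22–35. The integral of (e − 25)/8 from 25 to 33 is 4, plus 2 days beyond 33, so (4 + 2)/13 = 46%.

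| Assumed duration (days) | 7 | 14 | 21 | 28 | 35 |
|---|---|---|---|---|---|
| Onset Days 1–14 | 0% | 4% | 46% | 92% | 100% |
| Onset Days 7–21 | 4% | 43% | 89% | 100% | 100% |

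The onset windows are suggested by 5.4.2; the durations are assumptions. The loss is concentrated in reactions of about three weeks or less.

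**4. Dose-cut subjects (illustration).** Suppose that k of 75 subjects reach a component score of 3 before Week 4, score 1 at Week 4 after a dose cut, and everyone else scores 1 throughout. The Week 4 column shows mean 1.00 and 0% severe. The mean of subject maxima is 1 + 2k/75.

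| k | Share severe at maximum (k/75) | Mean of maxima |
|---|---|---|
| 4 | 5% | 1.11 |
| 8 | 11% | 1.21 |
| 15 | 20% | 1.40 |

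The values of k are invented to show the mechanism. The same subjects would also appear in the AE table with an intensity.

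**5. Can the documents size the loss?** The only human figure at 10% BID in the available text is 2 of 5 Phase 1B subjects with reversible skin reactions (5.6.1). That is 40%, with a Clopper-Pearson 95% interval of 5.3% to 85.3%, or about 4 to 64 of 75 subjects. It is too wide to use, and no timing is given there.

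**The case against.** The strongest reply is that much is already covered, and most of it stands.

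- **Early reactions are not simply unrecorded.** A reader might infer that they are. Under 15.1.2, any reaction needing a prescribed drug or a dose adjustment is an AE even if it stays within the field and has gone by Week 4. It carries a three-point intensity (15.2), which 17.4 summarises by cohort. That intensity rests on effect on daily activity, so it does not replace an LSR grade, but the event is not hidden.
- **Other traces exist.** Moisturiser in the field needs investigator approval (12.9.1), concomitant products are recorded at visits, and missed doses go in the diary. What leaves no trace is likely to be the mildest group.
- **Scoring at unscheduled visits may already be intended.** Sections 10.3.7 and 22.1 refer to every subsequent or study visit, and 7.4(b) asks for re-assessment. One cannot say that such visits go unscored; the text leaves it to the site.
- **Week 4 is a reasonable time to look.** In the 13-week minipig study, reactions on continued dosing were near their plateau by then, and erythema was similar in vehicle animals. Phase 2a, with early visits, found no clinically significant LSR change, though at half the daily dose.
- **Some text is unseen.** The Phase 1B summary (5.5.3) is not in the text available to this review and may give onset times. Section 17.2 defers analysis details to the SAP, which may add a maximum score, and 15.3 defers AE instructions to a Safety Monitoring Plan.

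These points narrow the concern. They do not supply a Week 2 skin question or a required grade before a dose change.

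**Conclusion.** The concern holds in a limited form, as a low-cost improvement to consider. Following the plan exactly leaves 28 of 84 treatment days without a scheduled LSR score or structured skin question. Two losses follow: field-confined reactions that settle before Week 4 with no prescription, dose change or unscheduled visit, and the peak LSR grade of subjects whose dose was changed.

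The documents do not support a numerical estimate of either loss. The capture percentages and dose-cut means rest on assumed durations and counts. Nor do they support the inference that the trial will materially understate local reactions, or will favour one cohort; both are possible and neither is shown. Confidence is high on the schedule facts and medium on their practical importance.

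**What to change.** 1. **Section 12.7, Week 2 call.** Ask whether the subject has had any skin reaction, itch or pain in the Treatment Field since the first dose. Record yes/no, dates, and subject-rated worst itch and pain. Report this apart from investigator LSR scores. On the first onset assumption above, with the call on Days 12–18, the call and Week 4 together would pick up at most 97%, 98% and 100% of reactions lasting 7, 14 and 21 days. That is a ceiling: it assumes perfect recall and that every call is made, whereas 12.7 asks for calls only where possible.
2. **Sections 7.4 and 12.8.** State that LSR is scored at any unscheduled visit and, where the subject is seen, before a dose change.
3. **Section 17.4.** Beside the by-visit summary, add each subject's maximum post-baseline LSR (component and composite) by cohort, including unscheduled scores.

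The cost is one short CRF item at about 150 calls already planned, and one extra table. The tolerability profile may look slightly less favourable. No visit is added. Grading redness, swelling or crusting by telephone is unnecessary, because the anchors in 22.1 need an examiner, and so are extra visits triggered by telephone scores.
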